### **3. RECORDING OF ADVERSE EVENT AND/OR SERIOUS ADVERSE EVENT**

When an AE/SAE occurs, it is the responsibility of the Investigator to review all documentation (e.g., hospital progress notes, laboratory reports, and diagnostics reports) related to the event.

The Investigator will then record all relevant AE/SAE information in the CRF.

It is **not** acceptable for the Investigator to send photocopies of the participant's medical records to Medical Monitor in lieu of completion of the eCRF.

There may be instances when copies of medical records for certain cases are requested by the Sponsor. In this case, all participant identifiers, with the exception of the participant number, will be redacted on the copies of the medical records before submission to the Sponsor.

The Investigator will attempt to establish a diagnosis of the event based on signs, symptoms, and/or other clinical information. Whenever possible, the diagnosis (not the individual signs/symptoms) will be documented as the AE/SAE.

#### **3.1. ASSESSMENT OF SEVERITY**

The adverse event severity grading scale for the NCI CTCAE (v5.0) will be used for assessing adverse event severity. [Table 1](#) will be used for assessing severity for adverse events that are not specifically listed in the NCI CTCAE.

**Table 1 Adverse Event Severity Grading Scale**

Grade	Severity
1	Mild; asymptomatic or mild symptoms; clinical or diagnostic observations only; or intervention not indicated
2	Moderate; minimal, local, or non-invasive intervention indicated; or limiting age-appropriate instrumental activities of daily living a
3	Severe or medically significant, but not immediately life-threatening; hospitalization or prolongation of hospitalization indicated; disabling; or limiting self-care activities of daily living b,c
4	Life-threatening consequences or urgent intervention indicated d
5	Death related to adverse event d

NCI CTCAE = National Cancer Institute Common Terminology Criteria for Adverse Events.

Note: Based on the NCI CTCAE (v5.0), which can be found at:

[https://ctep.cancer.gov/protocolDevelopment/electronic\\_applications/docs/CTCAE\\_v5\\_Quick\\_Reference\\_8.5x11.pdf](https://ctep.cancer.gov/protocolDevelopment/electronic_applications/docs/CTCAE_v5_Quick_Reference_8.5x11.pdf)

a Instrumental activities of daily living refer to preparing meals, shopping for groceries or clothes, using the telephone, managing money, etc.

b Examples of self-care activities of daily living include bathing, dressing and undressing, feeding one's self, using the toilet, and taking medications, as performed by patients who are not bedridden.

c If an event is assessed as a "significant medical event," it must be reported as a serious adverse event (see Section 6 of this appendix for reporting instructions), per the definition of serious adverse event in Section 2.

d Grade 4 and 5 events must be reported as serious adverse events (see Section 6 for reporting instructions), per the definition of serious adverse event in Section 2. Grade 4 laboratory abnormalities would only be reported as SAEs if these meets one or more of the conditions outlined in Section 2 (Definition of Serious Adverse Events) of [Appendix 2](#).

### 3.2. ASSESSMENT OF CAUSALITY

Investigators should use their knowledge of the participant, the circumstances surrounding the event, and an evaluation of any potential alternative causes to determine whether or not an adverse event is considered to be related to the study treatment, indicating "yes" or "no" accordingly. The following guidance should be taken into consideration:

- Temporal relationship of event onset to the initiation of study treatment.
- Course of the event, considering especially the effects of dose-reduction, discontinuation of study treatment, or reintroduction of study treatment.
- Known association of the event with the study treatment or with similar treatments.
- Known association of the event with the disease under study.
- Presence of risk factors in the participant or use of concomitant medications known to increase the occurrence of the event.
- Presence of non-treatment-related factors that are known to be associated with the occurrence of the event.

For participant receiving combination therapy, causality will be assessed individually for each protocol-mandated therapy.

#### **4. FOLLOW-UP OF AES AND SAEs**

The Investigator is obligated to perform or arrange for the conduct of supplemental measurements and/or evaluations as medically indicated or as requested by the Sponsor to elucidate the nature and/or causality of the AE or SAE as fully as possible. This may include additional laboratory tests or investigations, histopathological examinations, or consultation with other health care professionals.

If a participant dies during participation in the study or during a recognized follow-up period, when possible, the Investigator will provide the Sponsor with a copy of any postmortem findings including histopathology.

New or updated information will be recorded in the originally completed eCRF.

The Investigator will submit any updated SAE data to the Sponsor within 24 hours of receipt of the information.

#### **5. IMMEDIATE REPORTING REQUIREMENTS FROM INVESTIGATOR TO SPONSOR**

Certain events require immediate reporting to allow the Sponsor to take appropriate measures to address potential new risks in a clinical trial. The Investigator must report such events to the Sponsor immediately; under no circumstances should reporting take place more than 24 hours after the Investigator learns of the event. The following is a list of events that the Investigator must report to the Sponsor within 24 hours after learning of the event, regardless of relationship to study treatment:

- Serious adverse events
- Adverse events of special interest (AESI)
- Pregnancies (see Section 8.3.5)

The Investigator must report new significant follow-up information for these events to the Sponsor immediately (i.e., no more than 24 hours after becoming aware of the information). New significant information includes the following:

- New signs or symptoms or a change in the diagnosis.
- Significant new diagnostic test results.
- Change in causality based on new information.
- Change in the event's outcome, including recovery.
- Additional narrative information on the clinical course of the event.

Investigators must also comply with local requirements for reporting serious adverse events to the local Health Authority and IRB/EC.

## **5.1 REPORTING REQUIREMENTS OF SERIOUS ADVERSE EVENTS, AND ADVERSE EVENTS OF SPECIAL INTEREST**

### **Events that Occur prior to Study Treatment Initiation**

After informed consent has been obtained but prior to initiation of study treatment, only serious adverse events caused by a protocol-mandated intervention should be reported. The Serious Adverse Event/Adverse Event of Special Interest Reporting Form provided to Investigators should be completed and submitted to the Serious Adverse Event Responsible immediately (i.e., no more than 24 hours after learning of the event).

### **Events that Occur after Study Treatment Initiation**

For reports of serious adverse events and adverse events of special interest (Section 8.3.6) that occur after initiation of study treatment (Section 8.3.1), Investigators should record all case details that can be gathered immediately (i.e., within 24 hours after learning of the event) on the appropriate Adverse Event of Special Interest/ Serious Adverse Event eCRF form and submit the report via the electronic data capture (EDC) system. A report will be generated and sent to the Sponsor's Safety Risk Management department.

In the event that the EDC system is unavailable, the Clinical Trial Adverse Event/ Special Situations Form provided to Investigators should be completed and submitted to the Serious Adverse Event Responsible immediately (i.e., no more than 24 hours after learning of the event).

Once the EDC system is available, all information will need to be entered and submitted via the EDC system.

### **Reporting of Post-Study Adverse Events and Serious Adverse Events**

If the Investigator becomes aware of any other SAE occurring after the end of the AE reporting period, and if the event is believed to be related to prior study treatment, the event should be reported directly to the Sponsor or its designee, either by faxing or by scanning and emailing the Clinical Trial Adverse Event/Special Situations Form using the fax number or email address provided to Investigators.

## **5.2 *SPECIAL SITUATIONS (OVERDOSE, MEDICATION ERROR, DRUG ABUSE, AND/OR DRUG MISUSE)***

Overdose (accidental or intentional), medication error, drug abuse, and drug misuse (hereafter collectively referred to as "special situations"), are defined as follows:

- Accidental overdose: accidental administration of a drug in a quantity that is higher than the assigned dose
- Intentional overdose: intentional administration of a drug in a quantity that is higher than the assigned dose
- Medication error: accidental deviation in the administration of a drug (*e.g., wrong drug, expired drug, accidental overdose, underdose, wrong dosing schedule, incorrect route of administration*)
- Drug abuse: intentional excessive use of a drug that may lead to addiction or dependence, physical harm, and/or *psychological harm*
- Drug misuse: intentional deviation in the administration of a drug that does not qualify as drug abuse

In cases where drug is to be self-administered by the participant, drug misuse could involve the drug being administered to someone other than the participant.

*After initiation of study drug, special situations associated with basmisanil/matching placebo and any associated AEs will be reported until 28 days after the final dose of study treatment.*

*Special situations, regardless of whether they result in an AE, should be reported on the Special Situations eCRF. If there are any associated AEs, each event should be recorded separately on the Adverse Event eCRF.*

*Special situations and any associated AEs should be reported within 30 days after the Investigator becomes aware of the situation. However, if an associated AE fulfills seriousness criteria or qualifies as an AESI, both the event and the special situation should be reported to the Sponsor immediately (*i.e.*, no more than 24 hours after the Investigator becomes aware of the event), as described in Section 5.1 of this appendix.*

## **6. EXPEDITED REPORTING TO HEALTH AUTHORITIES, INVESTIGATORS, INSTITUTIONAL REVIEW BOARDS, AND ETHICS COMMITTEES**

The Sponsor will promptly evaluate all serious adverse events and *AESI* against cumulative product experience to identify and expeditiously communicate possible new safety findings to investigators, IRBs, ECs, and applicable Health Authorities based on applicable legislation.

To determine reporting requirements for single adverse event cases, the Sponsor will assess the expectedness of these events through use of the reference safety information in the document listed below:

Drug	Document
Basmisanil	Basmisanil Investigator's Brochure

The Sponsor will compare the severity of each event and the cumulative event frequency reported for the study with the severity and frequency reported in the applicable reference document.

Reporting requirements will also be based on the Investigator's assessment of causality and seriousness, with allowance for upgrading by the Sponsor as needed.

## **Appendix 3** **Procedures for Recording Adverse Events**

Investigators should use correct medical terminology/concepts when recording adverse events on the Adverse Event eCRF. Avoid colloquialisms and abbreviations.

Only one adverse event term should be recorded in the event field on the Adverse Event eCRF.

### **1. DIAGNOSIS VERSUS SIGNS AND SYMPTOMS**

A diagnosis (if known) should be recorded on the Adverse Event eCRF rather than individual signs and symptoms (e.g., record only liver failure or hepatitis rather than jaundice, asterixis, and elevated transaminases). However, if a constellation of signs and/or symptoms cannot be medically characterized as a single diagnosis or syndrome at the time of reporting, each individual event should be recorded on the Adverse Event eCRF. If a diagnosis is subsequently established, all previously reported adverse events based on signs and symptoms should be nullified and replaced by one adverse event report based on the single diagnosis, with a starting date that corresponds to the starting date of the first symptom of the eventual diagnosis.

### **2. ADVERSE EVENTS OCCURRING SECONDARY TO OTHER EVENTS**

In general, adverse events occurring secondary to other events (e.g., cascade events or clinical sequelae) should be identified by their primary cause, with the exception of severe or serious secondary events. However, medically significant adverse events occurring secondary to an initiating event that are separated in time should be recorded as independent events on the Adverse Event eCRF. For example:

- If vomiting results in mild dehydration with no additional treatment in a healthy adult, only vomiting should be reported on the eCRF.
- If vomiting results in severe dehydration, both events should be reported separately on the eCRF.
- If a severe gastrointestinal hemorrhage leads to renal failure, both events should be reported separately on the eCRF.
- If dizziness leads to a fall and subsequent fracture, all three events should be reported separately on the eCRF.

All adverse events should be recorded separately on the Adverse Event eCRF if it is unclear as to whether the events are associated.

### **3. PERSISTENT OR RECURRENT ADVERSE EVENTS**

A persistent adverse event is one that extends continuously, without resolution, between participant evaluation timepoints. Such events should only be recorded once on the

Adverse Event eCRF. The initial severity of the event should be recorded, and the severity should be updated to reflect the most extreme severity any time the event worsens. If the event becomes serious, the Adverse Event eCRF should be updated to reflect this.

A recurrent adverse event is one that resolves between participant evaluation timepoints and subsequently recurs. Each recurrence of an adverse event should be recorded separately on the Adverse Event eCRF.

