**Table 5 Objectives and Endpoints for Part 1**

Objectives	Endpoints
Primary	

 
• To evaluate the effects of 52 weeks of treatment with basmisanil on core symptom domains of Dup15q syndrome (language and social skills) and daily functioning
 
	
 
• Vineland-3: Adaptive Behavior Composite
 

Secondary	
Efficacy	

 
• To evaluate the effects of 52 weeks of treatment with basmisanil on: 
 
○ Motor function
 
○ Cognition
 
○ Language
 
○ Social skills
 
○ Clinician global impression of severity and change
 
○ Challenging behaviors
 
 
 
	
 
• Vineland-3 gross and fine motor subdomains
 
• MSEL gross and fine motor domains
 
• MSEL visual reception domain
 
• Vineland-3 expressive and receptive communication subdomains
 
• MSEL expressive and receptive language subdomains
 
• Vineland-3 play and leisure time and interpersonal relationships subdomains
 
• Dup15q CGI-S and Dup15q CGI-C
 
• ABC-2-C domain scores
 

Safety	

 
• To evaluate the tolerability and safety of 52 weeks of treatment with basmisanil
 
	
 
• Incidence, nature, and severity of AEs and SAEs
 
• Incidence of treatment discontinuations due to AEs
 
• Incidence of laboratory abnormalities based on hematology, clinical chemistry, and urinalysis test results
 
• ECG changes from baseline; incidence of abnormal ECG assessments
 
• Change from baseline in all seizure frequency, duration, and type of seizure as reported in a seizure diary by caregivers
 

ABC-2-C = Aberrant Behavior Checklist – Second edition – *Community Version*; AE = adverse event; Dup15q CGI-C = Dup15q syndrome *Clinician Global Impression of Change* scale; Dup15q CGI-S = Dup15q syndrome *Clinician Global Impression of Severity* scale; MSEL = Mullen Scales of Early Learning; SAE = serious adverse event; Vineland-3 = Vineland Adaptive Behavior Scales–Third Edition.

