## 4. **STUDY DESIGN**

### 4.1 **OVERALL DESIGN**

An overview of the study design is provided in Section 1.2.

This study consists of two parts. Part 1 is a multi-center, randomized, double-blind, placebo-controlled, parallel group study to evaluate the safety, efficacy, and pharmacodynamics of 52 weeks of basmisanil treatment in children and young adolescents aged 2 to 14 years with Dup15q syndrome. Part 2 is a 2-year optional OLE on basmisanil.

In Part 1, approximately 90 participants will be randomized 2:1 to receive oral treatment with either basmisanil or placebo for 52 weeks (BID on the first day of treatment in the clinic (Day 1) and three times a day [TID] for the remaining study duration; see Section 4.3 for justification).

Randomization will be stratified by age group (2 to 5 years vs. 6 to 14 years), number of copies of the 15q11.2-q13.1 region (3 copies vs. 4 copies), and epilepsy (presence vs. absence). All participants who have completed 52 weeks of treatment in Part 1 will be offered the option to roll over directly to the OLE (Part 2) without completing the follow-up visit in Part 1 (no treatment gap). No new patients will be enrolled in the OLE. All participants in Part 2 will receive oral treatment with basmisanil for approximately 2 years (see Section 4.3 for justification).

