#### **4. ABNORMAL LABORATORY VALUES**

Not every laboratory abnormality qualifies as an adverse event. A laboratory test result should be reported as an adverse event if it meets any of the following criteria:

- Accompanied by clinical symptoms.
- Results in a change in study treatment (e.g., dosage modification, treatment interruption, or treatment discontinuation).
- Results in a medical intervention (e.g., potassium supplementation for hypokalemia) or a change in concomitant therapy.
- Medically relevant in the Investigator's judgment.

It is the Investigator's responsibility to review all laboratory findings. Medical and scientific judgment should be exercised in deciding whether an isolated laboratory abnormality should be classified as an adverse event.

If a medically relevant laboratory abnormality is a sign of a disease or syndrome (e.g., alkaline phosphatase and bilirubin 5 times the upper limit of normal [ULN] associated with cholecystitis), only the diagnosis (i.e., cholecystitis) should be recorded on the Adverse Event eCRF.

If a medically relevant laboratory abnormality is not a sign of a disease or syndrome, the abnormality itself should be recorded on the Adverse Event eCRF, along with a descriptor indicating if the test result is above or below the normal range (e.g., "elevated potassium", as opposed to "abnormal potassium"). If the laboratory abnormality can be characterized by a precise clinical term per standard definitions, the clinical term should be recorded as the adverse event. For example, an elevated serum potassium level of 7.0 mEq/L should be recorded as "hyperkalemia".

Observations of the same medically relevant laboratory abnormality from visit to visit should not be repeatedly recorded on the Adverse Event eCRF, unless the etiology changes. The initial severity of the event should be recorded, and the severity or seriousness should be updated any time the event worsens.

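### AE severity is updated on one undated record, so for an event running past Day 365/366 the worst grade reached in Part 1 cannot be recovered

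*Combined protocol and SAP*

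**What the plan says.** **Collection.** Appendix 3, Section 3 says of persistent AEs: "Such events should only be recorded once on the" Adverse Event eCRF. It continues, "The initial severity of the event should be recorded", and then "the severity should be updated to reflect the most extreme severity any time the event worsens". If the event becomes serious, the same form is updated. For laboratory AEs, Appendix 3, Section 4 says "the severity or seriousness should be updated any time the event worsens", and Section 5 has the same rule for vital signs. Appendix 2, Section 4 adds: "New or updated information will be recorded in the originally completed eCRF". None of these sections asks for the date on which a grade changed.

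**The switch.** Under Section 4.1, participants who complete Part 1 may "roll over directly to the OLE (Part 2) without completing the follow-up visit in Part 1 (no treatment gap"). Section 6.3.1 puts everyone in Part 2 on open-label basmisanil, whatever their Part 1 arm. Under Section 8.3.1, AE reporting runs from the first dose to 28 days past the last one, with no break at Day 366.

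**Analysis.** Table 5 lists "Incidence, nature, and severity of AEs and SAEs" as a Part 1 secondary safety endpoint, and Table 6 lists it again for Part 2. Section 9.3.3 tabulates Part 1 AEs by treatment group. Table 13 sets the safety population equal to the ITT population, which is allocated by randomized arm. The re-assignment clause below that table covers incorrect treatment during Part 1, not the planned switch. Section 9.4 leaves Part 2 methods to a separate technical document.

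**The concern.** A single record updated to its worst grade is a sound convention when a participant stays on one treatment. Here, a former placebo participant can have an AE that began on placebo and reached its worst grade on basmisanil. Onset belongs to one treatment and grade to the other, and the record has no date to separate them.

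At stake is the severity part of the randomized safety comparison, in a trial with a small placebo arm. If first exposure to basmisanil worsens events that were present on placebo, and those grades enter the Part 1 tables, the placebo arm looks worse than it was and the contrast with basmisanil shrinks.

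**Working it through.** **1. What one record can show.** Take three event histories, all with onset in Part 1 at grade 1 and all still present at Day 365/366 (constructed for illustration, using the grading scale in Appendix 2, Section 3.1).

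| History | Course in Part 1 | Course in Part 2 | True worst grade in Part 1 | Required record |
|---|---|---|---|---|
| A | rises to 3 | no further rise | 3 | initial 1, updated 3 |
| B | stays at 1 | rises to 3 | 1 | initial 1, updated 3 |
| C | rises to 2 | rises to 3 | 2 | initial 1, updated 3 |

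The required record is the same in all three rows, while the quantity that a Part 1 severity table needs is 3, 1 or 2. Using the updated grade overstates B and C. Using the initial grade understates A and C. Selecting records by onset date keeps all three and does not change the grade attached to them.

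**2. Can open-label time exist when Part 1 is analysed?** Section 9.3.2 places the primary efficacy analysis after all participants have finished 52 weeks or withdrawn. Enrollment is staggered: under Sections 4.1 and 4.1.2.2, at least 9 Stage 1 participants must complete 4 weeks of dosing and be reviewed before Stage 2 opens. Early entrants can therefore be in Part 2 by then. No separate timing or AE cut-off is given for the Part 1 safety tables.

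**3. Scale.** The plan has no figure on this issue. Its one derived figure, about 81 evaluable participants (Section 9.1), reproduces as 90 × (1 − 0.10) = 81, but nothing here depends on it. Assume that all 90 are dosed and the 2:1 split is exact:

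- Placebo: 90 × 1/3 = 30. Basmisanil: 90 × 2/3 = 60.
- Let k_P and k_B be the numbers whose Part 1 record crosses a grade cut-off only through Part 2 worsening, and who have no other qualifying Part 1 event.
- Shift in the placebo rate = k_P/30. For k_P = 1, 2, 3 and 5 this is 3.3, 6.7, 10.0 and 16.7 percentage points.
- Shift in the risk difference (basmisanil minus placebo) = k_B/60 − k_P/30.

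The shift is zero when k_B = 2 × k_P, that is, when the same proportion of each arm is affected. It is negative, so basmisanil looks safer, when placebo is affected proportionally more. Only the former placebo arm meets the drug for the first time at Day 366, so a difference is plausible. The documents give no value for k_P or k_B.

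**The case against.** The strongest reply is that Appendix 3 governs data entry, not tabulation. A reader might infer that the plan counts such an event in the placebo arm at its worse grade. No section says so. That would require Part 1 tables built on randomized arm and the latest grade, with no cut-off at the first Part 2 dose. Sections 9.3.2 and 9.4 leave detailed methods to documents outside the protocol. This stands against the stronger reading. It does not close the gap, because an analysis document cannot recover a date that the protocol never requires.

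Other replies, and what stands of each:

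- *Initial severity is recorded.* True, so it would be wrong to say that the plan simply discards the starting grade. But the initial grade is not the worst grade in Part 1 (histories A and C).
- *A new record may be allowed.* Appendix 3, Sections 4 and 5 permit re-recording when the cause of a laboratory or vital-sign finding changes, and some investigators may apply that to the switch. Section 3 has no such exception. Appendix 2, Section 1 treats worsening of a preexisting condition as an AE, but Appendix 3, Section 8 defines preexisting by the screening visit.
- *Seriousness can be dated.* Largely true: Appendix 2, Sections 5 and 5.1 require reports within 24 hours. The point is mainly about grade.
- *Changes may be dated elsewhere.* The eCRF is not shown, and an audit trail or the medical record may hold dates. The protocol does not require them for analysis.
- *Consequences are limited.* AE summaries are descriptive. Laboratory shift tables use test results, and ECG, EEG and seizure-diary data are analysed separately (Section 9.3.3). New-onset or new-type seizures, QTc and renal findings are AEs of special interest (Section 8.3.6). This limits the damage to AE grade tables.

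**Conclusion.** The point holds as a gap in collection. Under the visible rules, the worst Part 1 grade of an AE that crosses Day 365/366 and worsens later cannot be recovered from the required data. Part 1 severity tables by randomized arm can therefore carry open-label worsening back into either arm, including placebo.

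The size is bounded only per event: about 3.3 percentage points on a placebo rate for each affected participant, assuming 30 dosed. The net effect on the comparison depends on how the arms differ, and the number affected is unknown. It is limited to AEs that are ongoing at the switch, worsen before the Part 1 data cut, and occur in participants without a qualifying event already.

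Two further inferences are not supported. One is a particular attenuation of the risk difference: that needs assumed worsening rates, full rollover and full open-label follow-up at the Part 1 cut, none of which the plan gives. The other is that such worsening drops out of the Part 2 results: Section 9.4 plans analyses of the combined database and does not assign AEs to a part by onset date.

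**What to change.** 1. In Appendix 3, Sections 3 to 5, add one of two rules: record the date of every change in grade or seriousness; or, when an AE ongoing at the first Part 2 dose worsens or becomes serious after that dose, leave the Part 1 record at its Part 1 grade and enter the worsening as a new AE with its own start date, linked to the first.
2. In Section 9.3.3, state that Part 1 tables use the worst grade and seriousness reached before the first Part 2 dose. For participants who do not enter Part 2, the existing reporting period applies.
3. If linked records are chosen, say how a linked pair is counted in the combined Part 1 and Part 2 analysis.

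The cost is a sentence or two in each place and an eCRF completion instruction. The downside is a few extra AE records and, with linked records, slightly higher Part 2 counts. The change belongs at collection, ideally before the first participant rolls over, because dates of worsening are hard to reconstruct later.
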